Protocol Title: Metabolic, Hormonal, and Physiological Characterization of Isoenergetic High Intensity Interval Training and Moderate Intensity Continuous Training in Adults with Type I Diabetes

Principal Investigator: *[name]
Associate Professor
Director, Applied Physiology Laboratory
Department of Exercise & Sport Science
[name]
[contact]
Email: [contact]*

Co-Investigators: *[name]
Cary C. Boshamer Distinguished Professor of Nutrition & Medicine
Chair, Department of Nutrition*

*M. [name]
Medical Director, Diabetes Care Center Clinical Trials Unit
University of North Carolina*

*[name]
Resident Physician
Department of Family Medicine
University of North Carolina*

Funding Sponsor: *NC Diabetes Research Center
Bowman Gray Center for Medical Education
[name]
[name]*

Version Date: September 17, 2021

NCT Trial: **NCT04664205**

Study Summary

Title	Metabolic, Hormonal, and Physiological Characterization of Isoenergetic High Intensity Interval Training (HIIT) and Moderate Intensity Continuous Training (MICT) in Adults with Type I Diabetes (T1D)
Short Title	HIIT and T1D
Methodology	Randomized Controlled Cross-Over Design
Study Duration	Two years
Study Center(s)	Single site
Objectives	
Aim 1: To compare the metabolic responses immediately and 1 hr after one bout of HIIT compared to MICT matched for total energy expenditure, vs no exercise (control; CON) in 14 adults with T1D.
 
Aim 2: To evaluate key counter-regulatory/metabolic hormones during and after HIIT, MICT, and CON sessions and the change in glycemia (using continuous glucose monitoring and glycemic cutpoints [<70 mg/dL, 70-180 mg/dL, >180 mg/dL]) for 48 hrs post exercise.
 
Aim 3: To explore the modulatory effect of physiological variables on metabolism, including biological sex, lean body mass and visceral fat (measured from dual energy x-ray absorptiometry).

Number of Subjects	14 (7 females, 7 males)
Treatment Regimens	All subjects will undergo three conditions, in a randomized order: 
 1) HIIT 2) MICT 3) CON
Statistical Methodology	
Aim 1: Principal Component Analysis for metabolomics data; two-way ANOVA [regimen (HIIT vs. MICT vs. CON) \times time (base vs. immediate post vs. 1h post)]
 
Aim 2: Two-way mixed-factorial ANOVA for counterregulatory hormones; Comparison of area under the curve across all trials for CGM, aggregated over 24 hrs
 
Aim 3: Spearman correlations between metabolomic outcome and physiological variables)

Abbreviations and Definition of Terms

Abbreviations and Definitions of Terms	
Abbreviation:	Formal Title:
HIIT	High Intensity Interval Training
MICT	Moderate Intensity Continuous Training
T1D	Type 1 Diabetes
CON	Control (no exercise)
CGM	Continuous Glucose Monitoring
HbA1c	Hemoglobin A1c
VO ₂ peak	Peak Oxygen Consumption
PAR-Q+	Physical Activity Readiness Questionnaire
BMI	Body Mass Index
4C Model	Four Compartment Model
FM	Fat Mass
%fat	Percent Body Fat
LM	Lean Mass
DXA	Dual-energy x-ray Absorptiometry Total Body Scan
BIS	Bioelectrical Impedance Spectroscopy
VT	Ventilatory Threshold
HR	Heart Rate
HR _{max}	Maximal Heart Rate
TIR	Time-in-Range
CHO	Carbohydrate
PRO	Protein
FAT	Fat
NDSR	Nutrient Data System for Research
ELISA	Enzyme-Linked Immunosorbent Assay
MVPA	Moderate-Vigorous Physical Activity
EDTA	Ethylenediaminetetraacetic acid
W	Watts
EXSS-IRB SOP	Exercise and Sport Science Institutional Review Board Standard Operating Procedures
DAIDS	Division of AIDS
AE/SAE	Adverse Event/Serious Adverse Event
UPIRSO	Unanticipated Problems Involving Risks to Subjects or Others
DSMB	Data and Safety Monitoring Board
APL	Applied Physiology Laboratory

1 Introduction

This document is a protocol for a human research study. This study will be conducted according to US and international standards of Good Clinical Practice (FDA Title 21 part 312 and International Conference on Harmonization guidelines), applicable government regulations and Institutional research policies and procedures.

1.1 Background

Cardiovascular disease is the most frequent cause of premature death and morbidity in type 1 diabetes (T1D).^[1] Overweight and obesity are growing concerns in individuals with T1D, potentially contributing to an increased risk for cardiovascular disease in this already vulnerable population. Exercise is an essential strategy for the management of health and comorbidities in T1D, reducing the severity of cardiovascular risk factors, such as obesity, blood pressure, lipid lipoprotein profile, and systemic inflammation.^[2] Regular exercise has been shown to help individuals with T1D reduce hemoglobin A1c (HbA1c) and improve blood lipid profiles, body composition, and endothelial function.^[3, 4] People with T1D who exercise more frequently also tend to have lower total daily insulin needs and experience fewer diabetes related complications.^[5, 6] Despite the benefits of exercise, less than 20% of patients with T1D report participation in consistent exercise having to overcome a number of barriers, including fear of hypoglycemia, unpredictable glycemic excursions with exercise, inadequate knowledge about exercise management, and lack of time.^{5, 7, 8}

High intensity interval training (HIIT), an exercise strategy where short intense exercise bouts are interspersed with brief recovery periods, requires as little as 10 minutes of exercise per session and results in rapid improvements in cardiorespiratory fitness and mitochondrial function.⁹ Our preliminary evidence¹⁰⁻¹² suggests that HIIT is a promising approach for maximizing cardiorespiratory and metabolic adaptations in individuals who are metabolically challenged because of obesity or physical inactivity, including insulin sensitivity and glycemic control.^{13, 14} A single bout of HIIT in these individuals activates mitochondrial biogenesis, a key mechanism for regulating cardiometabolic adaptations and fuel utilization before and after exercise. Metabolomics and proteomics have previously been used to understand the acute effects of exercise in healthy populations;¹⁵ but the physiologic mechanisms by which HIIT may induce adaptations in T1D has not previously been evaluated. Carbohydrate oxidation increases with an increase in exercise intensity, whereas fat oxidation is accelerated during more moderate intensity exercise. The extent to which exercise intensity influences amino acid metabolism is unclear.¹⁶ Metabolism of carbohydrate and fats are also regulated by various hormones including insulin, glucagon, cortisol, and catecholamines. These perturbations in metabolism are elevated for several hours following moderate-high intensity exercise; a metabolomics profile in T1D with varied intensity exercise has not previously been explored and could be of great importance with respect to glycemic control both during and in the hours following exercise in individuals with T1D. Importantly, these metabolic responses may also be influenced by obesity, biological sex and the amount and quality of lean mass, an organ with high glucose disposal rates. Studies with HIIT in individuals with T1D are more limited; available evidence suggests HIIT provides similar or superior improvements in cardiorespiratory fitness and endothelial function compared to moderate intensity exercise, without a detrimental decline in blood glucose.^[7, 8]

Dynamic Multiparametric Metabolic Response to Exercise, known as metabolomics, is a growing area of research that allows for earlier identification of metabolic dysfunction and creates a better understanding of how lifestyle interventions, such as diet and exercise, influence the metabolic profile (**Figure 1**).^[9] Acylcarnitines have been identified as the strongest metabolic biomarker of the exercise trained state.^[10, 11] Increased systemic concentrations of plasma acylcarnitines occurs in conditions of dysfunctional fatty acid oxidation, such as insulin resistance and obesity.^[10, 12] Systemic acylcarnitine concentrations decrease with exercise training and increased cardiorespiratory fitness, suggesting enhanced mitochondrial oxidative capacity.^[11] Succinate, Krebs Cycle intermediates, and amino acids have also been associated with improved insulin sensitivity in response to high-intensity exercise.^[11] Acutely, targeted metabolomics approaches have shown concentrations of non-esterified fatty acids to be increased for up to two hours following HIIT, suggesting a shift toward greater lipid metabolism.¹⁶ Chronically, previous results from our lab show promising

[figure not shown]

Figure 1. Theoretical model for proposed project.

improvements in skeletal muscle energetics with HIIT, specifically reducing acylcarnitine concentrations after six weeks of HIIT in patients with knee osteoarthritis (NCT03039452; in press).[11]

To date, only a few studies have examined the effects of HIIT in T1D, reporting similar or superior improvements in fitness level and endothelial function from HIIT, compared to traditional MICT, without a detrimental decline in blood glucose.^{23, 24} Improving our knowledge of the metabolic and counter-regulatory responses to HIIT in those with T1D is needed to identify effective and feasible exercise strategies to help regulate glycemic control, while also effectively managing T1D associated cardiometabolic comorbidities. As a result of the high prevalence of overweight and obesity, and concomitant exacerbation of cardiovascular and metabolic disease among individuals with T1D, there is a major need to identify effective and feasible behavioral interventions designed to mitigate health risks and optimize glycemic control.

2 Study Objectives

Specific Aim 1: To compare the metabolic responses immediately and 1 hr after HIIT compared to MICT matched for total energy expenditure, vs no exercise in 14 adults with T1D. Metabolism will be defined as energy expenditure (via indirect calorimetry), carbohydrate metabolism (tricarboxylic acid intermediates), and fat metabolism (acylcarnitines, respiratory exchange ratio).

Specific Aim 2: To evaluate key counter-regulatory/metabolic hormones (i.e. cortisol, lactate, glucagon, and insulin) during and after HIIT, MICT, and control (CON) sessions and the change in glycemia (using continuous glucose monitoring and glycemic cutpoints [<70 mg/dL, 70 - 180 mg/dL, >180 mg/dL]) for 48 hrs post exercise.

[figure not shown]
Specific Aim 3: To explore the modulatory effect of physiological variables on metabolism, including biological sex, lean body mass and visceral fat (measured from dual energy x-ray absorptiometry). Body fat percentage, lean mass, and visceral fat will be used to characterize the sample; the relationship of these variables with metabolomic intermediates will be assessed.

3 Study Design

3.1 General Design

In a randomized controlled cross-over design, fourteen adults (7 females, 7 males) with T1D of at least 1-year duration and HbA1c $<9\%$ will undergo three conditions, in a randomized order: 1) high intensity interval training exercise session (HIIT) at 90% peak oxygen consumption (VO_2 peak); 2) moderate intensity exercise session (MICT; 65% VO_2 peak; or 3) a control session (CON; no exercise) (Figure 2).

Subjects will be asked to arrive to the laboratory after an overnight fast (8 hrs) and their usual dose of insulin administered the day prior, with no morning mealtime insulin the day of testing. The lower and higher limit for pre-exercise (i.e. fasted) glucose concentration (i.e. 10 minutes prior to the exercise start time) will be set at 90 and 250 mg/dL, respectively, and the session will be rescheduled if the pre-exercise glucose value is not in range or if hypoglycemia (blood glucose: <70 mg/dL) occurs within an hour of exercise start time. Subjects will also be asked to arrive to testing sessions following a 12 hour fast from caffeine and alcohol and to abstain from physical activity for 24 hours prior to testing. Subjects will complete one electronic contact (phone/email screening) and up to five in-person sessions (enrollment; baseline testing; three conditions [HIIT, MICT, CON]) over the course of 4 weeks

All data collection will be conducted by the Principal Investigator and Research Assistants. All subjects will report to the Applied Physiology Laboratory in [name] for consenting, enrollment, testing, and exercise sessions.

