3.2 Primary Study Outcomes

The primary study outcomes include circulating metabolites that will be measured using an untargeted mass spectrometry-based platform with fasting concentrations of up to 1500 endogenous metabolites related to mitochondrial function, fatty acid oxidation, insulin resistance, and glucose regulation. Targeted metabolomics analysis for acylcarnitines and amino acids will be completed; non-targeted analyses will also be performed as an exploratory analysis, in order to promote the identification of unknown metabolites in addition to the known biology and physiology. Responses will be collected prior to, immediately post, and 1 hr post exercise.

3.2a. Secondary Study Outcomes

Counterregulatory hormones (cortisol, lactate, glucagon) will be evaluated at the same time points. Glucose will be continuously monitored for 48 h post exercise. , and glycemic control through 48 hrs after HIIT, compared to MICT versus a no exercise CON.

3.2b. Tertiary Study Outcomes

Tertiary outcomes will evaluate the influence of biological sex and physiological outcomes (i.e. body composition, lean mass, visceral fat) on the metabolomics profile of these subjects.

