Subjects will be familiarized with the cycle ergometer for the HIIT and MICT exercise. For familiarization, participants will practice a few intervals and cycle a few minutes at the individualized intensity for each respective exercise. They will also be asked, and provided with instructions, to practice one session (HIIT or MICT) on their own, under a usual fed state, prior to their visit to the lab. Each practice session will occur with CGM and Garmin physical activity monitoring (described below). The sessions should mimic those of the actual exercise session; 5-10 bouts of HIIT will be recommended; MICT time frame will be based on specific calculations (described below), approximately 15-25 min. This is included to provide the research team insight into potential glucose excursions prior to the lab-based exercise session in a fasted state. Our laboratory team has successfully implemented a similar 'home-based' HIIT intervention in healthy and clinical populations, with no adverse events [IRB: 18-2393 (Endometrial Cancer); 16-0829 (Knee osteoarthritis); 15-1150 (Bone marrow transplant patients); 14-2398 (Anterior Cruciate Ligament Reconstructive patients); 13-3515 (patients with cardiovascular disease risk factors)].

Visit 3-5: Randomized Treatment Regimen: (~90 minutes to 120 minutes)

At baseline testing, subjects will be randomized to one of three treatment regimens: 1) HIIT; 2) MICT; 3) CON (no exercise). Subjects will repeat the following procedures for visits 3-5, except there will be no exercise session on the CON treatment session. Exercise sessions will occur in the Applied Physiology Laboratory on the UNC campus. **There will be a minimum of seven days between each exercise trial.**

Continuous Glucose Monitoring (CGM):

Participants will be given the option to monitor their interstitial glucose levels via their own CGM or through a Freestyle Libre Pro (Abbot Laboratories), which will be provided to them. In the case that they decide to use their own CGM, the researchers will request data only for the dates the participant is involved in the study. If a participant decided to use the Freestyle Libre Pro, sensor will be inserted subcutaneously 7 days before exercise for a period of up to 7 days post exercise. CGM metrics including percent time-in-range (TIR), percent time in hypoglycemia, and percent time in hyperglycemia will be evaluated during and 48 hrs post exercise.

Dietary Controls:

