Approximately 8 mL of blood sample (~ 1.5 teaspoons) using an EDTA tube will be taken upon arrival, immediately after exercise, and one-hour post exercise. CON intervention visit will consist of a single blood draw. Circulating metabolites will be measured using an untargeted mass spectrometry-based platform with fasting concentrations of up to 1500 endogenous metabolites related to mitochondrial function, fatty acid oxidation, insulin resistance, and glucose regulation. Analysis will be completed at the Duke Molecular and Physiology Institute Metabolomics Core, directed by [name]. Targeted metabolomics analysis for acylcarnitines and amino acids will be completed; non-targeted analyses will also be performed, in order to promote the identification of unknown metabolites in addition to the known biology and physiology. Counterregulatory hormones (cortisol, lactate, glucagon) and insulin will be analyzed. Samples will be centrifuged immediately upon collection, and aliquots of plasma will be immediately frozen at -80° C for batch analysis. All blood draws will be done in the Applied Physiology Lab by an individual trained in phlebotomy. The current lab group has previously received approval for intravenous blood draws from the antecubital region in several IRB#, to name a few: 16-1991, 15-0543, and 14-0777, with no adverse events reported.

Treatment Regimens: (~20- 30 minutes)

- 1) HIIT Intervention: A 2 minute self-selected warm-up, followed by 10 alternating sets of one minute of pedaling at a resistance corresponding to 90% of VO₂peak and one-minute in active recovery at 50 watts (W). The work completed during each interval will be calculated by multiplying the power output for each participant at 90% VO₂peak by the duration of the interval (60 s). The work completed during each recovery period will be added by multiplying the power output (50 W) by the duration of the recovery period (60 s). The work from both bouts will be added together and then multiplied by 10 to calculate the total amount of work that each participant will complete in the HIIT trial.
- 2) MICT Intervention: Subjects will cycle continuously at a workload corresponding to 65% VO₂peak (W) for a pre-calculated length of time (~20-30 minutes), equivalent to the work that will be completed in the HIIT trials.
- 3) CON Intervention: No exercise will be performed. Subjects will arrive to the lab following the same pre-testing guidelines followed for HIIT and MICT trials.

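### Participants' own exercise is limited only in the 24 hours before a session, so the 48-hour glucose window after CON (and after HIIT and MICT) is not protected from other exercise

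*Combined protocol and SAP*

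**What the plan says.** **Restriction.** Section 3.1 asks participants "to abstain from physical activity for 24 hours prior to testing". Section 4.1 (Treatment Regimens) defines the control by the visit and the rules leading up to it: "No exercise will be performed. Subjects will arrive to the lab following the same pre-testing guidelines followed for HIIT and MICT trials". Nothing is said about the hours after any of the three sessions. Section 3.5 excludes people who currently do HIIT, but no other regular exercise.

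**Outcome.** Specific Aim 2 (Section 2) follows glycemia "for 48 hrs post exercise". Section 3.2a says "Glucose will be continuously monitored for 48 h post exercise" and gives the comparison as "glycemic control through 48 hrs after HIIT, compared to MICT versus a no exercise CON". In Section 4.1 (Continuous Glucose Monitoring), the percentages of time in range, in hypoglycemia and in hyperglycemia "will be evaluated during and 48 hrs post exercise". Section 5.2 aggregates the glucose data over 24 hours and compares area under the curve across trials.

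**Practice bout.** Section 4.1 (Familiarization and Randomization) asks participants to "practice one session (HIIT or MICT) on their own, under a usual fed state, prior to their visit to the lab". It should resemble the real session and be done wearing the glucose sensor and the Garmin. The seven-day minimum appears under visits 3–5 and separates exercise trials. It does not mention practice.

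**Activity data.** The Garmin is worn from 7 days before exercise to up to 7 days after. Sections 4.1 and 5.2 treat its data as a possible covariate for the glucose analysis, with no variable, threshold or decision rule.

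**The concern.** For Aim 2, the comparator is 48 hours of glucose after a visit without exercise. A participant who goes for a run on the evening of the CON visit breaks no rule, and that window still counts as the no-exercise condition. The same run after HIIT or MICT mixes a second bout into the effect of the study bout. The practice bout raises a smaller version of the problem on the other side of the session: an exercise load close to the study's own may precede the first condition by little more than a day, including when that condition is CON.

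At stake are the precision, and possibly the size, of the exercise–CON contrast in 48-hour glycemia in a study of 14 people. Recording activity does not prevent it. Optional adjustment for activity after the session adjusts for something the condition may itself change, and leaves a modelling choice open until the data have been seen.

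**Working it through.** The plan gives no figure of its own here, so the check compares the time rules and then sizes the effect under stated assumptions.

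**1. Windows on one clock (session at 0 h).**
- Restricted by Section 3.1: −24 to 0 h.
- Outcome window in Sections 2, 3.2a and 4.1: 0 to +48 h.
- Overlap: 0 h. All 48 of the 48 hours are unrestricted. If only the 24-hour aggregate of Section 5.2 is analysed, all 24 of 24 are.

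**2. Practice bout.** Sensor (when study-supplied) and tracker start 7 days before exercise, and the 24-hour rule removes the last day. If practice is done in the lead-in to the first session (an assumption), 7 − 1 = 6 days are open, and the 24–48 h slot is 1 of these 6. The visits span 4 weeks (28 days) and two seven-day gaps use 14 of them. The calendar therefore neither forces practice into that slot nor prevents a longer gap. The bout precedes whichever condition comes first. The text speaks of one session and then of each practice session, so a later condition might be affected too.

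**3. How often a window might contain exercise (assumption).** If each day carries own exercise independently with probability h/7, the chance for a 48-hour window is 1 − (1 − h/7)²:
- h = 1: 1 − (6/7)² = 27%
- h = 2: 1 − (5/7)² = 49%

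Section 1.1 says fewer than 20% of patients with T1D exercise consistently, so low values are credible. Volunteers for an exercise study may differ, and one participant is 1/14 = 7% of the sample.

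**4. Effect on the contrast.** Let δ be the true exercise–CON difference. Assume that an own bout has the same effect δ, that effects add, and that own exercise occurs in a share p_EX of exercise windows and p_CON of control windows.
- Mean shift in the exercise window: δ + p_EX·δ
- Mean shift in the CON window: p_CON·δ
- Observed difference: δ × [1 − (p_CON − p_EX)]

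| Assumed excess, p_CON − p_EX | Contrast retained |
|---|---|
| 0 | 100% |
| 0.1 | 90% |
| 0.2 | 80% |
| 0.35 | 65% |

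**5. Equal rates.** With p_CON = p_EX = p the contrast is not biased under these assumptions, but noise is added. Each window gains variance p(1 − p)δ². If occurrence is independent between windows, a within-person difference gains 2p(1 − p)δ². At p = 0.2 this is 2 × 0.2 × 0.8 × δ² = 0.32δ², a standard deviation of √0.32 = 0.57δ. It is less if the same people exercise after every session.

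**6. What is not exposed.** Blood is drawn on arrival, immediately after exercise and 1 hour after, with a single draw at CON (Section 4.1, Metabolomics). Exercise after the visit cannot change those samples. Section 5.1 sizes the trial on carbohydrate oxidation, glucose, citric acid and succinate markers for HIIT versus MICT. There is no planned effect for the 48-hour glucose contrast from which to turn step 4 into lost power or extra participants.

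**The case against.** **The post-session period is free-living by design.** Participants resume usual insulin and usual care, diet is recalled rather than controlled, and activity is tracked as a possible covariate. This is a fair reading of the plan, and a restriction does make the window less natural. But Section 3.2a names a no-exercise comparator through 48 hours, and the plan does not say whether own exercise belongs in it.

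**Bias is not shown.** A reader might infer that participants train more after CON because they have not yet exercised, so that the contrast is pulled toward zero and late hypoglycemia is hidden. The 24-hour abstention applies before all three conditions, and no section gives exercise rates by condition. This objection stands: direction and size are conditional.

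**48 hours is an observation window, not a documented duration of effect.** Section 1.1 describes perturbations lasting several hours and Section 5.2 aggregates over 24 hours. It would be wrong to call a 24-hour abstention against a 48-hour outcome an internal contradiction. This stands for carry-over into a session. It does not answer the unprotected time after one.

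**Practice carry-over is weak.** The 24-hour rule keeps practice out of the last day, and Section 3.7 calls for equal sequences, so a first-period disturbance is spread over conditions and acts mainly as a period effect. This largely stands. A reader might also infer that carry-over touches only the regimen practised, but it reaches whichever condition comes first.

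**Absence may be incomplete.** Figure 2 and the practice instructions are not in the text reviewed and could contain a rule. If so, the point reduces to stating it in Sections 3.1 and 4.1.

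**Conclusion.** The gap is real on the text: no rule keeps the 48-hour glucose window after any condition free of other exercise, and no minimum gap follows the practice bout beyond the 24-hour abstention. It concerns the secondary 48-hour glucose outcome. A reader might infer that the primary metabolomics comparison is compromised, but post-session exercise cannot affect those samples.

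With equal rates of own exercise, the cost is mainly added within-subject variation. With an excess after CON, the contrast retained is about 1 − (p_CON − p_EX): 80% at an excess of 0.2. These figures assume that an own bout acts like a study bout and that effects add. The rates themselves are assumptions with no source in the documents. The evidence does not support saying that the control loses its meaning, or quoting an inflated sample size. This is a worthwhile, inexpensive improvement to the Aim 2 comparison, held with medium confidence as to its practical effect.

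**What to change.** 1. In Sections 3.1 and 4.1, ask participants to do no structured exercise for the 48 hours after each of HIIT, MICT and CON, with compliance checked on the Garmin already worn.
2. In Section 4.1, require the practice bout to end at least 48 hours before the first condition visit. With devices starting 7 days before, 7 − 2 = 5 days remain for practice. Applying the seven-day separation to practice would not fit, because practice would then fall at or before the start of device recording.
3. In Section 5.2, pre-specify a sensitivity analysis that repeats the glucose comparison without windows containing tracker-recorded exercise, with the definition of such exercise fixed in advance, and report the number of these windows by condition.

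**Cost.** A few protocol sentences and participant instructions, with no new device or visit. Participants give up their own workouts for two days after each session, and the post-session window becomes slightly less free-living. Excluding windows also costs data in a sample of 14, so that analysis should support the main comparison and not replace it.
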